## 5.2 Study Endpoints

## 5.2.1 Primary Endpoint

• One year relapse-free survival

## 5.2.2 Secondary Endpoints

- Remission duration
- Incidence and severity of adverse events
- Overall survival (one year)

## 5.3 Selection of Study Population and Enrollment Procedures

All subjects will be screened for eligibility; see Section 2: Schedule of Study Assessments and Section 5.12: Study Activities and Assessments for screening details. All patients must meet the qualifications as outlined below.

## 5.3.1 Inclusion Criteria

To be eligible to participate in this study, a patient must meet the following criteria:

- WHO-confirmed AML
- Age ≥18 years
- Between days 28 and 50 post transplantation at the time of initiation of the study drug
- ECOG performance status ≤ 2 (See Appendix A: ECOG Performance Status Scale)
- Life expectancy > 2 months
- Recipient of a myeloablative or non-myeloablative allogeneic HSCT
  - Conditioning regimen to be prescribed at investigator's discretion, but will be prospectively defined as myeloablative or non-myeloablative
- Stable engraftment, as defined by absolute neutrophil count (ANC) ≥ 1000/mm^3 and platelets ≥ 25,000/mm^3
- In morphologic remission (< 5% marrow blasts) based on BM biopsy performed +/- 5 days of day 28 posttransplantation
- Without clinical signs of active central nervous system disease
- For non-myeloablative transplants, ≥50% CD3 donor chimerism at screening
- High risk of relapse after HSCT, defined as the presence of minimal residual disease as measured by flow cytometry in the absence of evidence of morphologic disease on a bone marrow biopsy prior to HSCT

- Adequate organ function as indicated by the following laboratory values:
  - Aspartate aminotransferase (AST), alanine aminotransferase, (ALT) ≤ 3.0 x institutional upper limit of normal (ULN)
  - o Total bilirubin ≤ 2.0 x institutional ULN, unless documented Gilbert's syndrome
  - Either creatinine <1.5 x institutional upper limit of normal (ULN) or creatinine clearance >60 mL/min as calculated by institution's standard formula
- Serum/urine pregnancy test (for females of childbearing potential) that is negative within 72 hours prior to initiation of first dose of treatment (a patient is of childbearing potential if, in the opinion of the investigator, she is biologically capable of having children and is sexually active)
- Female patients of childbearing potential and sexually active males and female partners of childbearing potential must agree to use a highly effective method of contraception throughout the study and for at least 90 days after the last dose of assigned treatment.
- Subject is able to comply with study procedures and follow-up examinations.

# 5.3.2 Exclusion Criteria

- Concomitant treatment with other anti-neoplastic agents, with the exception, when clinically indicated, of prophylaxis in the post-transplantation setting with intrathecal chemotherapy
- Use of any other experimental drug or therapy within 28 days of baseline
- Inability to swallow or absorb drug
- Active uncontrolled acute fungal, bacterial, or other infection that is unresponsive to therapy at time of study drug dosing
- Unstable angina pectoris
- New York Heart Association Class III or IV heart failure
- QTc interval (using Fridericia's correction formula, QTcF, if prolonged) >470 msec
- Active cardiac arrhythmias with rapid ventricular response (defined as heart rate greater than 100 beats/minute)
- Known HIV infection
- Grade III/IV acute GVHD

- Current use or anticipated need for food or drugs that are known moderate/strong CYP3A4 inducers (See Table 1 and section 5.9.2: Prohibited Concomitant Therapy), with the exception of azole antifungals, which are permitted.
- Any medical, psychiatric, addictive or other kind of disorder which compromises the ability of the subject to give written informed consent and/or to comply with procedures.
- Pregnant or lactating females

## 5.3.3 Lifestyle Guidelines

All male and female patients who, in the opinion of the investigator, are biologically capable of having children and are sexually active, must agree to use a highly effective method of contraception consistently and correctly for the duration of the active treatment period and for at least 90 days after the last dose of investigational product. The investigator, in consultation with the patient, will select the most appropriate method of contraception for the individual patient from the permitted list of contraception methods, and instruct the patient in its consistent and correct use. The investigator, at each study visit, will confirm and document consistent and correct use. In addition, the investigator will instruct the patient to call immediately if the selected birth control method is discontinued or if pregnancy is known or suspected.

Highly effective methods of contraception are those that, alone or in combination, result in a failure rate of less than 1% per year when used consistently and correctly (i.e., perfect use) and include:

- 1. Abstinence
- 2. Established use of oral, injected or implanted hormonal methods of contraception
- 3. Correctly placed intrauterine device or intrauterine system
- 4. Male condom or female condom used with a spermicide (i.e., foam, gel, film, cream, suppository)
- 5. Male sterilization with appropriately confirmed absence of sperm in the post- vasectomy ejaculate
- 6. Bilateral tubal ligation or bilateral salpingectomy

In addition, special precautions will be taken to limit any potential photo irritation effect, by minimizing the patients'

exposure to light including high intensity UVb sources such as tanning beds, tanning booths and sunlamps. Patients should be advised to apply sunscreen/sunblock daily, and will be advised to report any reaction to sun exposed skin.

# 5.4 Duration of Study

All patients will be followed for 30 days after the last study treatment, and with annual phone calls for five years. It is anticipated that the study will be completed within four to five years.

# 5.5 Drug Administration

## 5.5.1 Premedication

No premedication is required.

## 5.5.2 PF-04449913

PF-04449913 will be provided to research subjects for the duration of their participation in this trial by Pfizer at no charge to them or their insurance providers. PF-04449913 is formulated in tablets containing 10 mg, 25 mg and 100 mg of study medication. The tablets are packaged in high-density polyethylene bottles, with protection from moisture and should be handled with care. Site personnel must ensure that patients clearly understand the directions for self-medication. Patients should be given sufficient supply to last until their next study visit. Patients should be instructed to keep their medication in the bottles provided and not transfer it to any other containers. PF-04449913 will be administered once daily and orally on a continuous basis for all patients. A cycle is defined as 28 days, regardless of missed doses or dose delays. PF-04449913 will be administered without adjustment for body size and irrespective of PO intake. Tablets must not be crushed or cut; they must be swallowed whole and not chewed. Patients should be instructed to self-administer their medication in the morning at approximately the same time each day and to not take more than the prescribed dose at any time. If a patient misses a day's dose entirely, they must be instructed not to "make it up" the next day. If a patient vomits any time after taking a dose, they must be instructed not to "make it up," but to resume subsequent doses the next

day as prescribed. If a patient inadvertently takes 1 extra dose during a day, the patient should not take the next dose of PF-04449913. If a medication error is accompanied by an AE, such as an overdose (accidental or intentional), as determined by the investigator, the AE is captured on an AE CRF page (see Section 5.13.3: Procedures for Recording Adverse Events).

# 5.6 Assuring Patient Compliance

Patients will receive all dosages of PF-04449913 by selfadministration in the outpatient setting, and will be instructed to continue if admitted to the hospital for reasons other than drugrelated toxicity. Patients will receive a diary to record the specific time each dose was taken and to record reasons for any missed doses. Patient compliance will be assessed on day 1 of cycles 2 and every cycle thereafter. Patients will be required to bring their diary and any remaining pills to clinic during this visit. Research personnel will count and record the number of used and unused drug at each visit and reconcile with the patient diary. Any unused PF-04449913 will be returned in compliance with 21 CFR 312.59.

# 5.7 Laboratory Criteria for Initiation of Treatment Cycles

Before any treatment cycle after cycle 1 may be administered, blood samples collected within 72 hours of the first dose of each cycle must meet the following criteria:

- Either creatinine ≤ 1.5 x ULN or creatinine clearance ≥ 60 mL/min as calculated by institution's standard formula
- Total bilirubin ≤ 2 x institutional ULN (unless documented Gilbert's syndrome)
- AST and ALT  $\leq$  5 x institutional ULN
- ANC > 1000/mm^3
- Platelets >25,000/m^3

# 5.8 Study Treatment Schedule

Patients will receive study treatment as detailed in Section 5.1: Overall Study Design, and assessments will be performed as outlined in Section 2: Schedule of Study Assessments. Routine disease assessments, as dictated by usual standard of care, will occur; there are no study-specific disease assessments. Patients will be taken off of the study if they meet criteria listed in Section 5.10.1: Stopping Rules.

# 5.9 Concomitant Therapy

## 5.9.1 Permitted Concomitant Therapy

Transfusion of blood and blood products, antibiotics, antiemetics and other standard supportive care medications are permitted if necessary. Azole antifungals (fluconazole, voriconazole, posaconazole, itraconazole and ketoconazole) may be used.

## 5.9.2 Prohibited Concomitant Therapy

Chemotherapy, immunotherapy and radiotherapy are prohibited.

The following information is based on results from in vitro studies with PF-04449913 and a drug-drug interaction study with a strong CYP3A4/5 inhibitor in healthy subjects.

CYP3A4/5 Inhibitors: Because inhibition of CYP3A4/5 isoenzymes were expected to increase PF-04449913 exposure and the extent of this interaction in humans was unknown, the use of moderate/strong CYP3A4/5 inhibitors was previously prohibited. In a healthy volunteer study, ketoconazole, a potent CYP3A4/5 inhibitor, produced a 2.4fold increase in plasma exposure and a 1.4-fold increase in peak plasma concentration of PF-04449913. Therefore a potential exists for drug-drug interactions with CYP3A4/5 inhibitors, and co-administration of PF-04449913 in combination with moderate/strong CYP3A4/5 inhibitors is not recommended. Selection of concomitant medication with no or minimal CYP3A4/5 inhibition potential is recommended. Moderate CYP3A4/5 inhibitors (Table 1) should be used with caution and only if considered medically necessary. If a moderate/strong CYP3A4/5 inhibitor is to be initiated in addition to PF-04449913, the guidance provided in Section 5.12.5.5 requiring additional EKG monitoring before, during and after starting the medication, electrolyte monitoring (including correction and re-checking values) and dose

modifications for QTcF prolongation per Section 5.10.2.2 must be followed. Azole antifungals are permitted to be administrated concomitantly with PF-04449913.

**CYP3A4/5 Inducers:** PF-04449913 metabolism may be induced when taking CYP3A4/5 inducers, resulting in reduced plasma concentrations. The impact of CYP3A4/5 inducers on PF-04449913 pharmacokinetics has not been studied in the clinic. Therefore co-administration of PF-04449913 in combination with any moderate/strong CYP3A4/5 inducers (representative medications in Table 1) is not permitted from study entry until study treatment discontinuation.

**Drugs with known risk of Torsade de Pointes (TdP):** PF-04449913 has been shown to have the potential to prolong the QTc interval in pre-clinical studies. In the first-in-patient study as single agent, Grade 3 QTcF prolongation was observed at the highest doses tested (400 mg and 600 mg). While the current clinical dose being

evaluated in this study is 100 mg, the concomitant administration of PF-04449913 and drugs with known risk of torsade de pointes is not recommended unless there are no alternatives. If a TdP drug is to be initiated in addition to PF-04449913 the guidance provided in Section 5.12.5.5 requiring additional EKG monitoring before, during and after starting the medication, electrolyte monitoring (including correction and re-checking values) and dose modifications for QTcF prolongation per Section 5.10.2.2 must be followed. QT prolonging medications should be avoided whenever

Prior or concurrent treatment with a Hedgehog inhibitor or concurrent treatment with other investigational agents not specified in the protocol is not permitted.

Use of warfarin is strongly discouraged if alternate medication (erg, low molecular weight heparin) can be substituted. Warfarin is a CYP3A4 substrate and drug interactions causing variability in INR are possible. Frequent monitoring of the INR is recommended in subjects taking warfarin. Dosage of warfarin should be adjusted as needed.

# 5.9.3 Table 1: Representative prohibited medications based on metabolic isoenzyme class.

possible.

Isoenzyme Class	Representative Drugs
Strong/moderate CYP3A4 inhibitors	aprepitant, clarithromycin, cimetadine, ciprofloxacin, conivaptan, diltiazem, erythromycin, fluconazole, grapefruit juice, itraconazole, ketoconazole, mibefradil, nefazodone, posaconazole, telithromycin, tofisopam, troleandomycin, verapamil and voriconazole (NOTE: antifungal azoles are permitted concomitant therapies)
Strong CYP3A4	carbmezapine, phenobarbital, phenytoin, rifampin,
inducers	rifabutin, rifapentin, St. John's Wort

However, because the lists of these agents are constantly changing, it is important to regularly consult a frequentlyupdated list such as:

http://medicine.iupui.edu/clinpharm/ddis/table.aspx; medical reference texts such as the Physicians' Desk

Reference may also provide this information.

# 5.10 Safety Plan

Patient safety will be assessed by reviewing AEs during planned visits and physical and laboratory examinations from the time the patient receives the first dose of study drug until 30 days after the patient's last study treatment. See Section 2: Schedule of Study Assessments, and Section 5.13: Definitions and Reporting Procedures for Adverse Events.

# 5.10.1 Stopping Rules

## 5.10.1.1 Individual Patients' Stopping Rules

Patients may be terminated from the study for the following:

- Noncompliance with the study protocol
- Morphological disease relapse, defined as having a bone marrow biopsy with > 5% leukemic blasts on the aspirate differential, the presence of peripheral blood blasts or extramedullary disease
- Patient decides to withdraw from the study
- ≥ Grade 3 AE that is possibly related to the study drug and does not resolve or improve within 28 days (see Section 5.10.2.2)
- Serious AE (SAE) related or possibly related to the study drug; disabilities, hospitalizations, prolongation of

hospitalizations or required interventions that are related to the transplant are excepted

- Development of unrelated illness which compromises further participation in the study
- Investigator determines that continuation on study is no longer in the best interest of the patient or a change in the patient's condition renders them ineligible for further treatment
- Subject is lost to follow-up despite reasonable efforts by the investigator to locate the subject.

## 5.10.1.2 Study Stopping Rules

The study will be suspended pending further review if, at any time, there is sufficient evidence to suggest that the true probability of hematopoietic toxicity attributable to the drug exceeds 25% or the true probability of severe GVHD exceeds 25%. Sufficient evidence will be defined as an observed failure rate whose lower one-sided 80% confidence limit exceeds the thresholds listed above (25% for hematopoietic toxicity and GVHD). Operationally, the study will be suspended if any of the following proportions are observed (or exceeded): 3/3-5, 5/6-10, 7/11-15, 9/16-20, 10/21-25, 11/26-28. The probabilities of early termination based on this stopping rule for various rates of true toxicity are shown in the table below. The probabilities are based on a simulation with 1,000 replications.

	Probability of Early Stopping Due to Toxicity				
Number of Patients	True Toxicity Rate				
	15%	25%	35%	45%	
28	0.0016	0.0693	0.375	0.787	

- If any of the above stopping rules is met upon enrollment of the next patient, accrual will be held until it is determined that no stopping rules will be met with currently enrolled patients.
- The study will continue until the last patient is followed 30 days beyond receiving the last dose of study drug. Annual

phone calls will be made as appropriate for 5 years after discontinuation of the study.

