## 5.10.3 Data and Safety Monitoring

AEs and SAEs will be reviewed on an ongoing basis to identify safety concerns, and the investigators may discontinue the study if excessive toxicity is observed. In addition, the study will be monitored by the Cancer Center's data safety and monitoring committee (DSMC) at times designated by the committee.

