## Oversight and Monitoring

The Principal Investigator will be responsible for monitoring the safety and efficacy of the trial, executing the DSM plan, and complying with all reporting requirements to local and federal authorities. This will be accomplished under the oversight of the Data & Safety Monitoring Committee (DSMC) of the University of Colorado Cancer Center (UCCC). The DSMC is responsible for monitoring data quality and patient safety for all clinical studies at UCCC. A summary of the DSMC activities follows:

- Conduct of internal audits
- Ongoing review of all reportable adverse events and all serious/unanticipated adverse events
- Supervises internal DSM boards and/or performs as an internal DSMB
- Has the authority to close and/or suspend trials for safety or trial conduct issues and may submit recommendations for corrective actions to the Associate Directors Executive Committee
- Performs routine internal monitoring of both investigator-initiated and cooperative group clinical trials

Data regarding number of subjects, significant toxicities, dose modifications, and responses will be discussed at regularly scheduled disease-oriented working group meetings. The discussion will be documented in the minutes and summaries will be submitted to DSMC quarterly.

The Principal Investigator at the Coordinating Center is responsible for the overall conduct of the study at all of the participating institutions and for monitoring its progress. The University of Colorado Cancer Center is the Coordinating Center for this study and this site will coordinate patient enrollment. There will be only one version of the protocol, and each participating institution will use that document. The protocol must not be rewritten or modified by anyone other than the Principal Investigator at the Coordinating Center. The Principal Investigator at the Coordinating Center is responsible for timely review of Adverse Events (AEs) to assure safety of the patients and for the review and timely submission of data for study analysis.

Each subject's treatment outcomes will be monitored at least monthly by a conference call with the investigators and CRAs from all participating institutions. Data regarding the number of patients, significant toxicities, dose modifications, and responses will be discussed and documented in meeting minutes.

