### 5.14 Statistical Methods and Sample Size Determination

The one-year probability of relapse-free survival for high-risk patients is roughly 30%. Using this as a null hypothesis, and speculating that the use of PF-04449913 will increase the one-year probability of relapse-free survival to 50%, we will require 50 patients to allow for a 90% power to detect this 20% difference, with a significance level of 0.05. We predict the need to screen roughly 60 patients to enroll 50 with high risk of relapse.

Kaplan-Meier estimates using SAS software will be utilized for statistical analysis.

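### Section 5.10.1.2 states one suspension rule in three forms that disagree: the 80% lower-limit definition, the printed counts and the printed early-stopping probabilities

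*Combined protocol and SAP*

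**What the plan says.** Section 5.10.1.2 (Study Stopping Rules) covers two endpoints, drug-attributable hematopoietic toxicity and severe GVHD, each with a 25% threshold. It gives the rule in three forms.

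- **Definition.** "The study will be suspended pending further review if, at any time, there is sufficient evidence" that the true rate is above the threshold, where "Sufficient evidence will be defined as an observed failure rate whose lower one-sided 80% confidence limit exceeds the thresholds listed above". No interval method is named.
- **Counts.** As the operational form, "the study will be suspended if any of the following proportions are observed (or exceeded): 3/3-5, 5/6-10, 7/11-15, 9/16-20, 10/21-25, 11/26-28".
- **Probabilities.** "The probabilities of early termination based on this stopping rule for various rates of true toxicity are shown in the table below". For 28 patients the table prints 0.0016, 0.0693, 0.375 and 0.787 at true rates of 15, 25, 35 and 45%, and adds: "The probabilities are based on a simulation with 1,000 replications".

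The other study-level safety powers carry no number. Section 5.10.3 says "the investigators may discontinue the study if excessive toxicity is observed", and its Oversight and Monitoring text says of the monitoring committee: "Has the authority to close and/or suspend trials for safety or trial conduct issues".

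**The concern.** The three forms are presented as the same rule, so each should be derivable from the others. If the counts are stricter than the definition, the study can carry on with results that the protocol itself calls sufficient evidence. If the table does not describe the counts, an ethics board or monitoring committee that relies on it has the wrong picture of how often the rule would suspend the study. This is the only numeric study-level safety boundary in the plan.

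**Working it through.** **Inputs**, all from section 5.10.1.2: threshold 0.25; one-sided 80% lower limit; counts 3, 5, 7, 9, 10 and 11 for the bands 3-5, 6-10, 11-15, 16-20, 21-25 and 26-28; true rates 15, 25, 35 and 45%. Every probability below is for one endpoint.

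**1. Definition against counts.** The exact lower 80% limit for x events in n patients is the 0.20 quantile of Beta(x, n − x + 1). It exceeds 0.25 exactly when P(X ≥ x | n, 0.25) < 0.20. At the band ends:

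| n | Smallest x meeting the definition | Its 80% lower limit | Printed count |
|---|---|---|---|
| 5 | 3 | 0.327 | 3 |
| 10 | 5 | 0.327 | 5 |
| 15 | 6 | 0.272 | 7 |
| 20 | 8 | 0.291 | 9 |
| 25 | 9 | 0.267 | 10 |
| 28 | 10 | 0.270 | 11 |

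At the four later band ends the printed count is one event too high. Inside the bands the gap widens, because one count is held across several sample sizes. For example, 3/6 (limit 0.269), 5/11 (0.295), 7/16 (0.310), 8/21 (0.276) and 9/26 (0.256) meet the definition but do not suspend. Over n = 3 to 28 the printed count equals the exact one at 3 sample sizes (4, 5 and 10). It is higher by 1 at 12, by 2 at 10 and by 3 at 1 (n = 16). It is never lower.

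Another interval method does not remove the gap. At 80%, the Wald band-end counts are 3, 4, 6, 7, 9, 10, and the Wilson and Jeffreys counts are 3, 4, 6, 7, 9, 9.

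**2. Counts against the table.** Start with the first band alone. Three or more events in the first five patients suspends the study:

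- at 25%: 10(0.25³)(0.75²) + 5(0.25⁴)(0.75) + 0.25⁵ = 0.0879 + 0.0146 + 0.0010 = 0.1035
- at 15%: 10(0.15³)(0.85²) + 5(0.15⁴)(0.85) + 0.15⁵ = 0.0244 + 0.0022 + 0.0001 = 0.0266 (unrounded sum)

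Both already exceed the printed totals for all 28 patients (0.0693 and 0.0016). A cumulative stopping probability cannot be smaller than its first part.

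For the full rule, carry the binomial distribution of the event count forward one patient at a time and remove the probability that reaches the printed count. At a 25% rate the six bands add 0.1035 + 0.0337 + 0.0150 + 0.0077 + 0.0209 + 0.0088 = 0.1896. Looks after every patient and looks only at band ends give the same answer: the count is constant within a band and events are not lost, so a boundary reached within a band is still reached at its end.

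| Stopping probability by patient 28 | 15% | 25% | 35% | 45% |
|---|---|---|---|---|
| Printed table | 0.0016 | 0.0693 | 0.375 | 0.787 |
| Printed counts, as written | 0.034 | 0.190 | 0.537 | 0.858 |
| One look at 28, P(X ≥ 11) | 0.0015 | 0.068 | 0.384 | 0.787 |
| Exact 80% definition, every patient | 0.110 | 0.400 | 0.759 | 0.951 |
| Exact 80% definition, band ends | 0.044 | 0.273 | 0.667 | 0.924 |

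With 1,000 replications, the printed row lies 5.6, 9.7, 10.2 and 6.4 Monte Carlo standard errors below the values for the printed counts. It lies within 0.6 standard errors of the single-look values. The table therefore appears to describe only the last boundary, 11/28; that origin is inferred from the fit and is not stated. Also, 0.0016 and 0.0693 are not multiples of 1/1,000, so they cannot be raw proportions from 1,000 replications.

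**3. Practical size of the first conflict.** The chance that a trial meets the exact definition by patient 28 but is never suspended by the counts is 0.076, 0.211, 0.223 and 0.093 at the four rates with a look after every patient. With looks at band ends only it is 0.011, 0.083, 0.131 and 0.066.

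**The case against.** The best reply is that the protocol introduces the counts as the operational rule, so sites have one instruction to follow, and that the rule is banded. At band ends the mismatch with the exact limit is at most one event, and the first two bands agree. The every-patient tally makes the gap look larger than a banded scheme intends. This is fair as to size. But the text promises suspension at any time, and four of the six band ends still disagree. If the counts govern, the 80% statement and the table are both wrong.

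A second reply points to the first bullet under the table, which holds accrual if a rule would be met on enrolling the next patient. On one reading, accrual stops whenever one more event would reach a boundary. That covers 19 of the 35 results (x, n) that meet the definition without reaching a printed count. With a look after every patient, it cuts the chance of neither suspension nor hold to 0.016, 0.066, 0.075 and 0.030. The bullet narrows the gap, but it is ambiguous and a hold is not a suspension. It does not cover 6/15, 8/20, 9/25 or 10/28.

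Third, the table triggers no action, and the investigators and the monitoring committee can act on their own judgement. This softens the consequence. It does not correct a stated operating characteristic, and discretionary powers do not replace the one numeric boundary.

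**Conclusion.** The point holds: section 5.10.1.2 is wrong as written. The mismatch between counts and table needs no assumption about the interval method or the look schedule. The printed counts stop with probability 0.190 at a 25% true rate against 0.0693 printed, about 2.7 times as often, and with 0.034 against 0.0016 at 15%, about 21 times as often. The mismatch between definition and counts is one event at four of six band ends under the exact limit, and larger within bands. Wald, Wilson and Jeffreys limits need the same or fewer events, so they do not help.

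The two errors differ in direction. Every printed count meets the 80% definition, so the counts never suspend without sufficient evidence; they fail to suspend in some cases where the definition is met. The table understates how often the counts would suspend at every rate.

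The figures assume independent patients with a constant event rate and outcomes known at each look. They are per endpoint. With two independent endpoints at 25% each, the printed counts would suspend with probability 1 − (1 − 0.1896)² = 0.34.

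**What to change.** Reconcile the section. State which form governs, which confidence-limit method is used and when the looks occur, then derive the rest from that choice.

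- **If the 80% definition governs:** print the counts it implies. With the exact limit, state stopping probabilities of 0.110, 0.400, 0.759 and 0.951 for a look after every patient, or 0.044, 0.273, 0.667 and 0.924 for looks at the six band ends only.
- **If the printed counts govern:** state 0.034, 0.190, 0.537 and 0.858, and replace or delete the 80% statement. A one-sided 95% Wilson or Jeffreys limit at the band ends reproduces all six counts. Whether that was the intention is not stated, and other methods at other levels also fit, so the sponsor should confirm the basis and not adopt this one by default.

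In either case, label the probabilities as sequential and per endpoint, correct the 1,000-replication statement, and clarify how the accrual-hold bullet works with the boundary. Also say whether the rule continues beyond patient 28, since section 5.14 states "we will require 50 patients to allow for a 90% power to detect this 20% difference". Which threshold or boundary is clinically right is for the sponsor and investigators.

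The cost is protocol wording and a short calculation, with no added patients or procedures. The stated chance of suspension at a 25% true rate will look less favourable: 0.190 to 0.400 per endpoint across the options above, against 0.0693 now.

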#### Secondary:

- Remission duration
- Incidence and severity of adverse events
- OS (one year)

STUDY DURATION: 5-7 years	TOTAL SAMPLE SIZE: 50

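### Section 5.10.1.2 prints suspension counts and stopping probabilities for only 28 of 50 patients; the counts do not follow the stated 80% criterion, and the probabilities do not describe the counts

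*Combined protocol and SAP*

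**What the plan says.** Section 5.10.1.2 (Study Stopping Rules) of the combined protocol and SAP contains four elements.

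- **A verbal rule with no patient limit.** "The study will be suspended pending further review if, at any time, there is sufficient evidence" that "the true probability of hematopoietic toxicity attributable to the drug exceeds 25% or the true probability of severe GVHD exceeds 25" per cent. Either endpoint is enough.
- **A definition of that evidence.** "Sufficient evidence will be defined as an observed failure rate whose lower one-sided 80% confidence limit exceeds the thresholds listed above", the threshold being 25% for both endpoints.
- **Counts.** "Operationally, the study will be suspended if any of the following proportions are observed (or exceeded): 3/3-5, 5/6-10, 7/11-15, 9/16-20, 10/21-25, 11/26-28".
- **An operating table.** It is titled "Probability of Early Stopping Due to Toxicity" and has one row, for 28 patients, indexed by a single true toxicity rate: 0.0016 at 15%, 0.0693 at 25%, 0.375 at 35% and 0.787 at 45%. The text attributes these to a simulation with 1,000 replications.

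The synopsis (Section 1) gives "TOTAL SAMPLE SIZE: 50", and Section 5.14 derives the same 50. No section explains the figure of 28, calls the first 28 patients a safety cohort, or gives a count for patients 29-50.

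**The concern.** The counts are what a study team would apply day to day, and this is the only numerical study-level safety boundary in the plan. It stops at 28 of 50 patients, which leaves 50 - 28 = 22 patients (44%) without a printed count. The table that should tell the ethics board and the data safety and monitoring committee (DSMC) how the rule behaves describes a trial of 28. It uses one event rate, although two endpoints can each suspend the study.

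The gap would be minor if the later counts could be read off the verbal criterion and the table were right as far as it goes. Neither holds. Two competent readers could therefore apply different boundaries after patient 28, and the stated risk of suspending at an acceptable 25% rate is too low even within the first 28.

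**Working it through.** **Inputs.** From Section 5.10.1.2: the counts, the 25% threshold, the one-sided 80% level, monitoring at any time, and the four table values. From Sections 1 and 5.14: 50 patients. I assume that each patient gives one known yes/no outcome per endpoint, independently of other patients.

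**Is 50 the intended size?** Section 5.14 tests 30% against 50% at 0.05 with 90% power. Declaring success at 21 or more of 50 gives one-sided alpha 0.048 and power 0.899. The 50 is supported, so the mismatch lies in the stopping section.

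**Step 1: reproduce the table.** A single look at the end gives P(X ≥ 11 | n = 28, p).

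For sequential use, let c(n) be the printed count and f(n,k) the probability of k events in n patients without a stop. Then f(n,k) = f(n-1,k)(1-p) + f(n-1,k-1)p for k < c(n), and the stopping probability is 1 - Σ f(28,k). Looking after every patient or only at 5, 10, 15, 20, 25 and 28 gives the same answer: the count is constant within a block and events only accumulate.

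| True rate | 15% | 25% | 35% | 45% |
|---|---|---|---|---|
| Printed | 0.0016 | 0.0693 | 0.375 | 0.787 |
| Single look at 28 | 0.0015 | 0.068 | 0.384 | 0.787 |
| Printed counts, sequential | 0.034 | 0.190 | 0.537 | 0.858 |

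Simulation error does not explain the difference. At 25% the standard error with 1,000 replications is √(0.0693 × 0.9307 / 1,000) = 0.008, while the difference is 0.190 - 0.069 = 0.121. Also, 0.0016 and 0.0693 are not multiples of 1/1,000.

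**Step 2: compare the counts with the criterion.** The exact (Clopper-Pearson) lower one-sided 80% limit exceeds 25% at the smallest x with P(X ≥ x | n, 0.25) < 0.20.

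| n (block end) | 5 | 10 | 15 | 20 | 25 | 28 |
|---|---|---|---|---|---|---|
| Printed | 3 | 5 | 7 | 9 | 10 | 11 |
| Exact 80% | 3 | 5 | 6 | 8 | 9 | 10 |
| Exact 90% | 4 | 5 | 7 | 9 | 10 | 11 |

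At 10/28, for example, P(X ≥ 10) = 0.138 and the 80% lower limit is 27.0%, so the stated definition is met one event before the printed count. The printed counts match a 90% limit at every block end except the first, where 3/5 reaches 89.65%.

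**Step 3: extend to 50.**
- Exact 80%: 10/29-30, 11/31-33, 12/34-37, 13/38-40, 14/41-44, 15/45-48, 16/49-50.
- Exact 90%: 11/29, 12/30-33, 13/34-36, 14/37-39, 15/40-43, 16/44-46, 17/47-50.

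At n = 30 the readings already differ, at 10 events against 12. The same recursion run to n = 50, per endpoint, gives:

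| True rate | 15% | 25% | 35% | 45% |
|---|---|---|---|---|
| Printed counts to 28, none after | 0.034 | 0.190 | 0.537 | 0.858 |
| Printed to 28, then 80% | 0.04 | 0.36 | 0.84 | 0.99 |
| As above, never below 11 | 0.04 | 0.34 | 0.84 | 0.99 |
| Printed to 28, then 90% | 0.035 | 0.26 | 0.74 | 0.98 |
| 80% criterion throughout (n = 3-50) | 0.11 | 0.47 | 0.88 | 0.99 |

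**Step 4: either endpoint, at n = 28.** The documents give no correlation between the endpoints. With equal true rates, complete overlap leaves the sequential values as they are. Independence gives 1 - (1 - s)², where s is the unrounded per-endpoint value: 0.066, 0.343, 0.785 and 0.980.

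**The case against.** The best defence is that a rule does exist after patient 28. The verbal criterion has no patient limit, and the counts only put it into practice. Section 5.10.3 adds ongoing review of adverse events, monthly calls, six-monthly reports and a DSMC with authority to suspend. This stands, and it rules out three stronger readings.

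- A reader might infer that the study cannot be suspended after patient 28, or that later toxicity is left wholly to discretion. The text does not support this: what is missing is a printed count and its operating characteristics, not monitoring.
- A reader might offer 10/28 followed by 22 events in 22 patients as a sequence that escapes the rule. It crosses no printed count, but the verbal criterion is already met at 10/28. The example shows that counts and criterion disagree, not that the rule is absent.
- A reader might combine the printed probabilities for two independent endpoints: 1 - (1 - 0.0693)² = 0.134 and 1 - (1 - 0.375)² = 0.609. Those inputs fit a single look at 28, so the results do not describe the sequential rule.

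It is also fair that one series of counts can serve both endpoints, since they share the 25% threshold, and that a table per endpoint is ordinary practice. A joint probability is a useful addition rather than a requirement.

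The defence fails at one point. The verbal criterion cannot fill the gap unambiguously, because the printed counts do not follow it.

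**Conclusion.** The point holds in this form: for 22 of 50 patients the plan gives neither a count nor a suspension probability, and its criterion, counts and table do not agree with one another within the first 28.

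In size, the printed table gives a per-endpoint suspension chance of 0.0693 at the 25% threshold, where the printed counts give 0.190. If either endpoint may suspend, the range is 0.190 to 0.343. At a true rate of 35%, the printed counts suspend with probability 0.537 by patient 28. Continuing a boundary to 50 gives 0.74 to 0.84, depending on whether the 90% or 80% level is used after patient 28.

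The sequential figures at 28 follow exactly from the printed counts under independent patients with outcomes known as they accrue. The figures to 50 depend on how the rule is extended, which the documents do not fix. The either-endpoint range assumes equal true rates and covers complete overlap to independence; negative association would go beyond it. The documents do not show which of the level, the counts or the figure of 28 is the error.

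**What to change.** 1. Reconcile the stated confidence level with the printed counts, and state the type of limit (exact or other) and the look schedule.
2. From the reconciled rule, print one non-decreasing series of counts to n = 50, and say that it applies to each endpoint separately. The two series in Step 3 are for reference. The 80% series should not simply be placed after 11/26-28, because the count would fall to 10 at patient 29; if the printed counts to 28 are kept, it should not go below 11.
3. Replace the table with sequential operating characteristics for n = 50, labelled per endpoint. Add the either-endpoint range if wanted, with its dependence assumption. State the number of replications, or compute the values exactly.

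The cost is one table and one short calculation, with no change to the endpoints or the 25% threshold. The downside is visible: the stated chance of suspension at a true rate of 25% rises from 0.0693 to about 0.26 (90% extension), 0.34 to 0.36 (80% extension) or 0.47 (80% throughout) per endpoint. The team should decide whether that is acceptable before fixing the rule.
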